To determine if this mHealth approach to promote healthy behaviors and healthy weight among children and their parents will be utilized by parents of 6-10 year old overweight/obese children, descriptive statistics will be used to examine adherence and scores on the treatment acceptability and treatment satisfaction surveys.

To obtain preliminary estimates of effect sizes, we will use mixed model analyses using an intent-to-treat approach. Model selection criteria using Akaike information criterion (AIC) will be employed to determine the best set of covariates, including, but not limited to, baseline demographic (e.g., sex, race) and anthropometric variables. T-tests based on the least squared means derived from the model are used to test the treatment effects. Responses such as change in body mass (kg and percent for the parents; BMIz for the children), physical activity, energy intake and diet quality, and treatment satisfaction and burden, will all be used in the mixed effect model and we will specifically include race and sex in the model to test if biological variables, such as sex, are associated with the outcomes.

Methods

Study Participants.

To be eligible for the study, the child must:

- Be 6-10 years of age
- Have at least one participating parent.
- Have a BMI percentile ≥ 85
- Be physically capable of exercise
- Be free of diseases that affect metabolism, body weight, and food intake, including type 1 or type 2 diabetes, HIV/AIDS, and cancer

To be eligible for the study, the parent must:

- Have a smart phone
- Be willing to use the smartphone for the mHealth intervention, including accessing the HealthTracker

Exclusion criteria for the child include:

- Significant cardiovascular disease or disorders via self-report from parent
- Other significant medical problems that would prevent them from engaging in regular physical activity.

Visits/Procedures

Below are the procedures that will be completed during study participation:

Procedure	Screening/ Baseline	Intervention	End of Study Follow-up
Assessment of or by the Parent			
Orientation Presentation	x		
Consent	x		
Height/Weight	x		x
Questionnaire (Medical History Survey)	x		
Acceptability Survey	x		
Pedometer (daily)		x	
RFPM (monthly)		x	
Treatment Satisfaction Survey			x
Assessment of Child			
Orientation Presentation	x		
Assent	x		
Height/Weight	x		x
Questionnaire (Lifestyle Survey, Treatment Satisfaction Survey)	x		x
Pedometer (daily)		x	
RFPM (monthly)		x	

Visits

Recruitment

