Using a study flyer we will advertise through the public library system, seek support of community leaders, issue personal appeals through social organizations, and place advertisements in places of congregation. Participants will also be recruited using traditional advertisement mediums if necessary, including newspaper, radio, television, and social media. We will actively recruit new potential participants from the Pre-PLACE and other pediatric studies, and we will submit a privacy board request to recruit participants who were recently deemed ineligible from the Pre-PLACE study and other recent pediatric studies.

Telephone Screen

We will perform an initial telephone screen to determine if the potential participant appears to meet eligibility criteria. Individuals deemed eligible from the telephone screen will then be scheduled for a screening visit and will receive the consent/assent form by email.

Screening/Baseline Visit

The screening visit will occur at a local YMCA or other community locations or in the participant's home. Participants will be formally oriented to the study by receiving detailed information on the purposes, goals, procedures, participant flow, and timeline. A parent will sign an informed consent. Participants ages 9-10 will sign a written assent form. Participants ages 6-8 will provide a verbal assent for participation. Parents will complete a program acceptability survey and complete a medical history questionnaire for their child. Children will complete the Lifestyle Survey. Height and weight measurements will be taken for both the child and parent. If they meet initial inclusion criteria based on the information collected, the parent/child dyad will meet with an interventionist to conduct or schedule an initial face-to-face counseling session.

Follow-up Assessment Visit

Parent-child dyads will return to a local YMCA or other community locations or in the participant's home for a follow-up visit at 14-16 weeks following the commencement of the intervention. Participants will have their height and weight measured and complete surveys.

Procedures

Program Acceptability/Treatment Satisfaction Surveys

Parents will complete a survey assessing program acceptability at screening and a survey assessing treatment satisfaction at the final assessment visit.

Medical History

Parents will complete a medical history questionnaire for their child.

Lifestyle Survey

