Children will complete a lifestyle survey assessing sleep, dietary and physical activity habits, and media use.

Anthropometry

Height and weight will be measured using a portable stadiometer and a scale. Measurements will be taken without shoes and recorded to the nearest 0.1 cm and 0.1 kg.

Intervention

Parent/child dyads will attend remote counseling sessions (each approximately 30 minutes) delivered over their Internet-connected device (e.g. smartphone, iPad/tablet, laptop, or desktop computer). A Pennington Biomedical counselor will deliver the lesson, review progress based on the objectively measured data available on the HealthTracker; more detail below), and provide individualized advice and problem-solving strategies for the parent and the child. Counselors will attempt to meet face-to-face with parents for the initial intervention session. Eight lessons will be delivered electronically via smartphone, iPad/tablet, laptop, or desktop computer. Over the course of the 14-16 week study, families will also receive weekly contact via smartphone (most interactions will be via FaceTime, Skype, or phone, but email and text communication will also occur). Each lesson will include an interactive component for the parent and child related to healthy eating and active play, as well as an interactive parenting training component. The lessons are based on the family treatment methods that effectively promote child and parent weight loss that is sustained for 10 years (Epstein et al., 1990; Epstein et al., 1981).

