The parent lessons are framed around these guiding principles: 1) weight and activity monitoring; 2) behavioral contracting with a goal of modeling appropriate strategies; 3) review of progress and problem-solving to address poor adherence to behavioral goals; and 4) food monitoring and goal setting for nutrient intake. Specific lessons will focus on how to motivate the child and how to manage non-compliance including praise and reward, positive reinforcement, selective ignoring, contracting, pre-planning for meals and physical activity, shaping behaviors, modeling, changes to the home environment, and facilitating social support for behavior change (Newton et al., 2011; Staiano et al., 2017). The dietary approach will employ food monitoring and goal setting for nutrient intake following the Traffic Light Diet, an effective approach for children and their parents within a clinically supervised, multi-component weight management program (Epstein et al., 1990). Foods are categorized as green, yellow, or red based on caloric density, and children and parents are given a goal to stay within a prescribed daily calorie range and to eat no more than four red foods each week. We will work with the parent to make systemic changes to what is served and how it is prepared in the home, focusing on preparation methods that decrease energy density and dietary fat, such as baking rather than frying foods. The physical activity approach will introduce free or inexpensive activity options and address barriers to physical activity. Counselors will work with parents to increase opportunities for play and activities that they and their children enjoy. We successfully used these lessons in prior and ongoing pediatric trials (Staiano et al., 2017; Williamson et al., 2005; Williamson et al., 2006) and have updated them over time. Specific targeted psychosocial constructs include increasing quality of life through active play and improving eating attitudes through modeling and introduction of healthy foods.

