The HealthTracker is Internet-based software that allows us to deploy the intervention as an EMI (Ecological Momentary Intervention) and Just in Time Adaptive Intervention (JITAI). The HealthTracker serves as the “hub” of intervention delivery for the counselors and participants, and it promotes treatment fidelity, ongoing communication and progress reviews between the remote counseling sessions, and structures intervention delivery for the counselors. Further, the HealthTracker remotely collects objective data, namely body weight, in near real-time and these data are used to facilitate behavior change during the mHealth intervention, consistent with learning theory. The intervention is

[figure not shown]
based on the theory of planned behavior and the theory of reasoned actions (Ajzen, 1991) by fostering an environment conducive to behavior change where participants' behavioral goals are clearly defined, self-efficacy is promoted, and behavior is regulated through objective data. The intervention also incorporates aspects of social cognitive theory (Bandura, 1988) by reinforcing behavior change and fostering personal agency, clear outcome expectations, and goal setting. Though the counselor and participant's relationship is remote and relies on communication technology, counselors are able to deploy motivational interviewing techniques to address decreases in motivation, which are inevitable in longer-term interventions (Patrick & Williams, 2012).

Component	Frequency	mHealth (HealthTracker with Virtual Counseling)
Lesson & Material Delivery	Weekly (Wk 1-4) Biweekly (Wk 6-14)	
 Counselor delivers 8 lessons to the child and parent during remote counseling sessions over video chat or phone call.
Body Weight	Daily (parent) Weekly (child)	
 Sent automatically from the Body Trace Scale in the home to the HealthTracker. Within minutes, the Weight Graph for the parent with individualized target weight zones are available for the parent and counselor on HealthTracker. Children will be asked to weigh weekly, therefore the child weight graph will be sent remotely to the parent once per week.
Physical Activity (steps/day)	Weekly	
 The Steps Graph for the parent, including individualized steps/day target, are available for the parent and counselor on HealthTracker. The step graph for the children will be sent remotely to the parent once per week

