Food Intake (kcal/day)	Monthly, with ~1 week of data per month	
 Weight graphs will be continually used as a proxy for adherence to energy intake targets. For nutrient information, parent captures own and child's food images using Remote Food Photography. Images are automatically transmitted via the SmartIntake app.^{50,51}

The intervention largely is based on our previous successes with an mHealth weight management intervention for adults called "**SmartLoss**" (Martin et al., 2015; Martin et al., 2016). SmartLoss is an EMI and JITAI that promotes behavior change via the real-time capture of objective body weight and activity (step) data from participants' home environment. These data are wirelessly transferred to the Internet where they are graphed in relation to the individual participant's weight and step goals by our software and sent back to participants via their smartphone (these graphs are also available for the counselor, see Figure).

One cornerstone of SmartLoss is the ability to objectively quantify adherence to energy intake goals based on observed body weight. To achieve this aim, we developed and validated differential energy balance equations (Thomas et al., 2010) that predict weight change over time for an individual based on a prescribed energy intake target. Our software generates individual **weight graphs** that display the expected amount of weight loss over time, and the model

[figure not shown]
Weight Graph Zone of Adherence (Parent).

also generates upper and lower bounds around predicted weight loss. As shown in Figure 3, this creates a “zone of adherence” and a participant’s body weight is plotted over time in relation to this zone. The participant is considered adherent to the diet if their weight falls within the zone; hence, change in weight serves as a proxy for energy intake/dietary adherence. This graphical feedback is used by counselors and participants to deploy different treatment strategies to modify energy intake to improve adherence.

Customization of the HealthTracker and the Intervention. The HealthTracker will be accessible 24 hours per day by counselors and parents anywhere that has Internet access (including mobile devices), and the data in the HealthTracker are available in near real-time. Parents will interact with the HealthTracker to review their step and weight graphs.

Figure 4. Weight Graph Zone of Adherence (Child).

Weight Graphs

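### The protocol describes no health check of the parent before the parent is given calorie, weight and step goals

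*Protocol*

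**What the plan says.** In the Protocol, Study Participants, the parent must own a smartphone and be willing to use it for the intervention. No other parent criterion is listed. The disease, exercise-capability and medical-problem criteria all belong to the child. That includes the cardiovascular exclusion, "Significant cardiovascular disease or disorders via self-report from parent", where the parent is only the informant.

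Under Screening/Baseline Visit, the parent is to "complete a medical history questionnaire for their child"; the Medical History section repeats that the form is about the child. The parent's height and weight are measured, with no threshold attached. If the initial inclusion criteria are met, "the parent/child dyad will meet with an interventionist to conduct or schedule an initial face-to-face counseling session", so counseling may begin at that same visit.

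The parent's own goals are set out in the Intervention text and component table:
- Diet: "children and parents are given a goal to stay within a prescribed daily calorie range".
- Weight: "the Weight Graph for the parent with individualized target weight zones".
- Activity: "The Steps Graph for the parent, including individualized steps/day target".

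Risks/Benefits to Subjects adds that parents as well as children will be asked to raise their activity gradually. It calls the risks of doing so rare, but names irregular heartbeat and heart attack among them. The SAP is silent on all of this.

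**The concern.** The parent receives the same kinds of goals as the child. The child is screened for conditions that would make those goals unsuitable; as described, the parent is not. A parent who is pregnant, has heart disease, or takes a drug that affects weight could be given a calorie range or step target without having been asked about it.

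Feedback during the intervention could add to this. The parent's weight relative to the zone is read as dietary adherence, and counselors and participants use it to "deploy different treatment strategies to modify energy intake to improve adherence". Nothing describes how weight gain from pregnancy or illness would be told apart from poor adherence. What is at stake is parent safety, not the study's scientific result.

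**Working it through.** The documents state no figure to reproduce. The check is a comparison of texts, followed by one illustration.

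**1. Is there any parent health criterion?** Study Participants lists two parent criteria, both about the smartphone, and gives exclusion criteria for the child only. Count of parent health criteria: 0.

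**2. Could the medical history cover the parent?** The procedures table puts the Medical History Survey in the parent block. However, that block's heading covers assessments made by the parent as well as of the parent, the child block has no medical history row, and two passages of text say the form concerns the child. Even if it did ask about the parent, no criterion or action is stated for the answer.

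**3. Could the telephone screen cover the parent?** It is described as checking the eligibility criteria, which by step 1 contain no parent health item.

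**4. Do other safeguards act as a check before goals are set?**
- Individualized advice and the initial face-to-face session (Intervention; Screening/Baseline Visit): an opportunity for disclosure, but no health inquiry is described.
- Weekly contact ("families will also receive weekly contact via smartphone"): during the intervention; again no health inquiry is described.
- Relief from weighing where contraindicated (Weight Graphs): concerns weighing, not diet or activity goals.
- The two weight-loss safety criteria (Weight Graphs): defined for children only.
- Adverse event reporting (Data Safety Monitoring Plan): follows an event.
- Interventionist mitigation, continual monitoring and withdrawal at the PIs' discretion (Risks/Benefits; Withdrawal of Subjects): general provisions, not a check before goals are set.

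**5. How likely is it that the question arises at all?** The documents give no prevalence, so p, the share of parents who are pregnant or have a diet or exercise contraindication, is assumed. The chance that at least one such parent enrolls is 1 − (1 − p)^n. The protocol's ceiling is n = 30; n = 20 is an assumed lower enrollment.

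| Assumed p | n = 30 | n = 20 | Expected number, n = 30 |
|---|---|---|---|
| 1% | 26% | 18% | 0.3 |
| 2% | 45% | 33% | 0.6 |
| 5% | 79% | 64% | 1.5 |
| 10% | 96% | 88% | 3.0 |

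For example, 1 − 0.95^30 = 1 − 0.215 = 0.785. The range is driven almost wholly by the assumed p. It describes the chance that such a parent is among those enrolled, not the chance of injury, and it does not allow for parents who disclose unprompted.

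**The case against.** The strongest reply is that the hazard is modest and the setting is not blind to it. The activity increase is gradual and measured by pedometer, the options include ordinary play, and no calorie deficit is stated for the parent. The expected-weight-loss description belongs to the earlier adult program, although the Weight Graphs section ties the parent's graph to the same figure. The protocol classes the study as minimal risk. Parents are oriented, consented and counseled, and those with a known condition can say so. A caution may also appear in the survey form, telephone script or consent pages, which we cannot see.

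Most of this stands, and it limits the point. A reader might infer that an affected parent would start a goal before anyone knew, or that every safeguard acts only after goals are set. The documents support neither. A parent may know their own condition, the weight zones and step target are individualized, and the text does not say whether goals come before or after the first counseling session. A reader might also take the percentages above as a risk of harm; they are not.

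What does not fall away is that an opportunity to disclose is not a question asked. The minimal-risk classification bears on how serious the gap is, not on whether it exists.

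**Conclusion.** The point holds as a minor safety improvement: the parent is given diet, weight and activity goals, and the protocol describes no parent health check before they are set. This rests on the protocol text alone and is subject to the unseen form, script and consent pages.

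Its size as harm cannot be stated, because the documents give neither the prevalence of contraindications among parents nor a rate of parent injury. The primary acceptability outcome is essentially unaffected. A reader might go on to infer a material distortion of the secondary parent body mass result. The documents give no inputs from which to show one, and the point does not depend on it.

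**What to change.** 1. At the screening visit, before any parent goal is set, have the parent complete a brief private self-report about themselves: pregnancy, cardiovascular disease or another exercise contraindication, and conditions or drugs that affect weight.
2. Set no weight-loss or increased-activity goal for the parent during pregnancy.
3. Refer any other contraindication to the existing medical investigator before that parent's calorie or step goal is set. The child's goals and the lessons proceed meanwhile, and the dyad stays enrolled.
4. Instruct parents to tell the counselor privately of a new pregnancy, illness or drug, so that goals can be changed.

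Cost: a few minutes per parent, a little medical-investigator time, and a short goal-setting delay for flagged parents only. The delay is a real one, because the first counseling session may take place at the screening visit.

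Routine health questions at every weekly contact are not needed. At 14–16 contacts for 30 dyads they would come to 14 × 30 = 420 to 16 × 30 = 480 inquiries, some in sessions shared with the child or by text. That raises privacy concerns and adds burden in a study whose primary outcome is acceptability. No additional analysis of parent body mass is called for.

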Study Title: Healthy Kids I-PAL

NCT #: NCT03297541

Document date: 08.24.17

Sample Size Justification

This protocol is a pilot & feasibility study that will provide data on acceptability, feasibility, and estimates of effect size for an R01 submission. A sample size of up to 30 dyads will provide sufficient data for feasibility and acceptability.

Planned Statistical Analyses

To determine if this mHealth approach to promote healthy behaviors and healthy weight among children and their parents will be utilized by parents of 6-10 year old overweight/obese children, descriptive statistics will be used to examine adherence and scores on the treatment acceptability and treatment satisfaction surveys. To obtain preliminary estimates of effect sizes, we will use mixed model analyses using an intent-to[1]treat approach. Model selection criteria using Akaike information criterion (AIC) will be employed to determine the best set of covariates, including, but not limited to, baseline demographic (e.g., sex, race) and anthropometric variables. T-tests based on the least squared means derived from the model are used to test the treatment effects. Responses such as change in body mass (kg and percent for the parents; BMIz for the children), physical activity, energy intake and diet quality, and treatment satisfaction and burden, will all be used in the mixed effect model and we will specifically include race and sex in the model to test if biological variables, such as sex, are associated with the outcomes.
